Social Cognitive Theory,⁹³ content focuses on providing information, increasing motivation to quit, and increasing self-efficacy to resist smoking temptations (**Table 2**) via presentation of objective data as well as hypothetical “real world” scenarios of particular relevance to PLWH smokers. Users are given tools and options to cope with smoking urges. NRT use is encouraged. **Online social network:** The PSFW+ community runs on open source forum software by Vanilla Forums. We created a full-featured discussion forum with unlimited categories and user profiles that is customized to look like the main site. Vanilla Forums enables single sign-on for a seamless experience between the static content and online community. PSFW+ users can create a user profile with a unique avatar or personal photo, and can create a profile “wall” on which other users may post comments, images, or video. The primary interface is a feed of discussion threads: users create discussions or polls, and other users may post comments to the discussion or answer the poll. Users can also exchange private messages. The **PSFW+ Community Guidelines** emphasize the importance of creating and maintaining a safe environment for people to exchange information and support. The guidelines also remind users that all content posted in the community is publicly available, and that the administrator may remove messages that are spam or solicitations. Users who persistently violate Community Guidelines will have their community profile removed from the site. Our experience with several online communities with thousands of users is that these occurrences are infrequent; should they occur during the study period, we will account for this in our analyses. Involvement of an experienced administrator is integral to managing these situations proactively to ensure the smooth operation and success of an online community,^{24,94} especially during its nascent phase. The **PSFW+ Community Administrator** will monitor all public discussions and comments on the community, encourage interactions between community members, review all reports of inappropriate content that do not follow the Community Guidelines (such as spam), and serve as the main liaison between technical staff and community members for any technical issues. The **PSFW+ Terms of Use** and **Privacy Policy** make explicit that all content posted in the community is publicly available information and users are legally responsible for any content they post on the site. The registration page states “By clicking Submit, I agree to the Positively Smoke Free Terms of Use and Privacy Policy” (available via hyperlink). The treatment of the unique privacy concerns of a PLWH online community and its attendant legal implications have been carefully considered and are discussed in detail in the Human Subjects section.

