[[In order to calculate the incremental cost per quit, we will compile the costs of website hosting and maintenance, payments to the community administrator and seed users, staff support required to make reminder phone calls, and receipts for nicotine patches. Research costs and development costs for PSFW+ and the portal page for the Control condition will not be included.]]

3.C.6. Data Analysis Plan and Sample Size Calculations

3.C.6.a. Preliminary Analyses. We will calculate descriptive statistics and perform bivariate analyses using t-tests (or nonparametric tests if needed), Chi Square tests (or Fisher's exact tests if needed), and Pearson (or Spearman) correlation coefficients to evaluate relationships among baseline measures (e.g., demographic characteristics), mediating variables (e.g., perceived social support) and outcome measures (7-day ppa). Due to randomization, we expect the two treatment groups to be balanced with respect to the baseline measures. However, baseline measures identified in bivariate analyses as statistically significantly (at the 0.05 level) associated with the outcome measures will be included in the corresponding regression models as covariates to increase statistical power.

[figure not shown]

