Missing data. We expect less than 10% missing data at any time. Under an intention-to-treat approach, participants who had been considered non-smokers up to the point of losing contact will be considered relapsers at future data points. Multiple imputation methods¹⁴⁶ will be used to deal with missing data, assuming a missing at random (MAR) mechanism; we will generate 10 multiple imputed datasets, analyze each dataset separately, and then combine the results across the 10 datasets using Rubin's method.

3.C.6.c. Specific Aim 2: Mediator Analyses. Aim 2 hypothesizes that greater social support mediates the intervention-cessation relationship. Figure 3 depicts our mediational model:

X represents treatment group, **Z** represents the hypothesized mediator (e.g., perceived social support), **Y** represents outcome (7-day ppa), **a** is the regression path between treatment group and mediator, **b** is the regression path between mediator and outcome, and **c'** is the regression path between treatment group and outcome controlling for the effect of the mediator. The 3-month assessment will be used for mediator **Z** and the 6-month measure of 7-day ppa will be used as the primary binary outcome **Y**. To increase statistical power of our mediation analysis we will use the product of coefficients method.¹⁴⁷ We will estimate the coefficient **a** by fitting a linear regression model with the putative mediator as the continuous outcome, treatment arm as the main predictor, and covariates identified in bivariate analyses as being associated with social support. We will estimate the coefficient **b** by using a logistic regression model with abstinence as the binary outcome, **Z** as the main predictor, and covariates identified in bivariate analyses as being associated with abstinence. We will then calculate the mediated effect as the corresponding product of these coefficients with standard error and 95% confidence interval estimated according to MacKinnon.¹⁴⁸ Since the sampling distribution of this product shows considerable skewness and kurtosis, interval estimation will be based upon bias-corrected and accelerated (BCA) bootstrap confidence intervals.¹⁴⁹ Potential mediators in Figure 1 will be analyzed separately, and additional analyses will be conducted to evaluate interaction effects.

Figure 3. Mediational Analyses

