3.C.6.d. Exploratory Aim: Moderator Analyses. We will examine potential moderators of the intervention-smoking cessation relationship (e.g., demographics, depression, anxiety). Effect modification analyses will be conducted by testing interaction terms between treatment group and selected variables. Interaction terms will be added to variables already in the regression models (3.C.6.b.). Subsequent stratified analyses will be performed to explore specific moderation effects. **Mediator Analyses.** Exploratory mediation analyses will follow the approach in 3.C.6.c.

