[[3.C.6.e. Sample Size Considerations: Aim 1. Using the mean abstinence rates in the SC arms in our two recent R21 trials (9.7%²¹ and 4.3%¹⁴), and up-adjusting the rate slightly in consideration of the attention-placebo, we estimate a 7-day ppa at 6 months in the control condition will be 7.5%. Our estimate of the efficacy of PSFW+ is based on research by our team²⁰ and others⁶² who have demonstrated that visits to an online community increase abstinence rates. In the BecomeAnEX outcome evaluation,²⁰ 7-day ppa at 6 months ranged from 11.1% (ITT) to 20.7% (responder only); individuals who visited the online community two or more times were more than twice as likely to be abstinent than those who never visited (OR=2.22, 95% CI 1.34-3.69, P=.002) controlling for a broad range of demographic, smoking, and psychosocial covariates. These results are consistent with An et al.⁶² who reported a near doubling of abstinence rates (OR=1.91) among individuals who used individual messaging in an online cessation program. The benefits of an online community are not simply for the minority who actively post; reading communications ("lurking") also has beneficial effects.^{150,151} Therefore, we estimate that PSFW+ combined with our intensive adherence strategies to promote engagement and utilization will increase abstinence rates by 2.05 times over control, yielding a 6-month quit rate of 15.4%. This estimate is deliberately conservative in that we have chosen to use as the base rate our estimate of control (7.5%) rather than the quit rate from our previous trial of PSFW (10.1%). This will ensure that we are adequately powered to detect treatment group differences between PSFW+ and control. Assuming abstinence rates of 15.4% and 7.5% in the PSFW+ and control conditions, respectively, 254 subjects in each arm will be necessary to achieve power of 0.8 with an alpha=0.05. Projecting a liberal 9.2% loss-to-follow-up based on our previous NIH-funded trials (R21CA163100-01, R21DA023362), we will randomize N=275 per arm.]]

Sample Size Considerations: Aim 2. We are able to detect a mediation effect (coefficient product) of small size

(with coefficient product parameters $a=0.14$, $b=0.14$) with at least 80% power for each mediator given our expected sample size of $N=508$ at 6 months.¹⁵²

3.C.7. Potential Problems and Solutions

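### Aim 2 estimates path b from a model that leaves out treatment arm, so the mediated effect a×b absorbs part of any direct effect of PSFW+

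*Combined protocol and SAP*

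**What the plan says.** Section 3.C.6.c defines three paths: a from treatment group (X) to mediator (Z), b from mediator to abstinence (Y), and c', which "is the regression path between treatment group and outcome controlling for the effect of the mediator". Z is taken at 3 months and Y at 6 months. Path a comes from a linear model of Z with treatment arm as main predictor. Path b is estimated "using a logistic regression model with abstinence as the binary outcome, Z as the main predictor"; the sentence continues "as the main predictor, and covariates identified in bivariate analyses as being associated with abstinence". The mediated effect is the product of the two coefficients, with a BCa bootstrap interval.

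Three other statements bear on the point:
- Section 3.C.6.a says which covariates the screening can bring in: "baseline measures identified in bivariate analyses as statistically significantly (at the 0.05 level) associated with the outcome measures will be included".
- Section 3.C.6.c adds that "Potential mediators in Figure 1 will be analyzed separately".
- Section 3.C.6.d applies the same method to the exploratory mediators: "Exploratory mediation analyses will follow the approach in 3.C.6.c".

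**The concern.** Arm is named in the model for a and missing from the model for b one sentence later. It cannot come in through the covariate screen, because it is not a baseline measure. The definition of c' implies an outcome model holding X and Z together, but no section specifies that model or says that b is taken from it. An analyst who follows the one instruction given for b fits it without arm.

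Randomisation does not protect b, because Z is measured after randomisation. If arm shifts Z (a ≠ 0) and shifts quitting by routes other than Z (c' ≠ 0), arm confounds the Z–Y association. The bias in b has the sign of a×c'. It pushes b away from zero when that sign matches b and pulls it towards zero, or past it, when the signs differ.

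The plan does not state that c' is non-zero, but its content makes that likely. The PSFW+ core content is also directed at "increasing motivation to quit, and increasing self-efficacy to resist smoking temptations". The Exploratory Aim names nicotine replacement use, intervention dose and self-efficacy as further mediators. Because mediators are analysed one at a time, every other route falls into c' for social support.

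Aim 2 is described as central. What is at stake is whether social support is credited with an effect that came by another route.

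**Working it through.** **Inputs from the plan**
- Abstinence 15.4% (PSFW+) and 7.5% (control), 254 per arm, α = 0.05, power 0.80; Aim 2 paths a = b = 0.14, at least 80% power, N = 508 (Section 3.C.6.e).
- Allocation 1:1, so Var(X) = 0.25 (Section 3.C.4.d).

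**The plan's own figures**
- Aim 1: the two-proportion formula (two-sided, no continuity correction) gives 254 per arm, power 0.800.
- Aim 2: "We are able to detect a mediation effect (coefficient product) of small size". With standardised paths, a continuous outcome and arm in the model for b, joint significance gives Φ(0.14×√508 − 1.96)² = Φ(1.195)² = 0.884² = 0.782. A simulation with the bias-corrected bootstrap gives 0.823. The stated 80% is therefore consistent with a model for b that includes arm.

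**Assumptions for the check**

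The plan gives no scale for 0.14. I read both values as standardised:
- a as a correlation: arm difference d = 2×0.14/√(1 − 0.14²) = 0.283 SD.
- b on the logit scale: 0.14×π/√3 = 0.254 log-odds per SD.
- Z = d·X + N(0,1); the intercept and c' are set so that the arms have 7.5% and 15.4% abstinence. At the planned size this gives c' = 0.742.

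**Large-sample b without arm**

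Linear guide: b without arm ≈ b + c'·d·Var(X)/Var(Z), with Var(Z) = 1 + d²/4 = 1.02. At the planned size this is 0.254 + 0.742×0.283×0.25/1.02 = 0.305. Numerical integration of the logistic model gives the exact limits:

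| d (SD) | true b | c' | b without arm | change |
|---|---|---|---|---|
| 0.14 | 0.254 | 0.778 | 0.276 | +9% |
| 0.283 | 0.254 | 0.742 | 0.300 | +18% |
| 0.5 | 0.254 | 0.687 | 0.329 | +30% |
| 0.283 | 0.254 | 0 | 0.254 | none |
| 0.283 | 0.254 | −0.742 | 0.202 | −20% |
| 0.283 | 0 | 0.809 | 0.054 | – |

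The c' = 0 and c' = −0.742 rows keep control abstinence at 7.5% but not the 15.4%. At the planned size a×b is 0.283×0.300 = 0.085 against 0.283×0.254 = 0.072. With no mediation, b without arm is 0.054, which is 21% of the planned 0.254.

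**Sensitivity to the scale of b** (d = 0.283, rates held at 7.5% and 15.4%): b = 0.14 gives +35%, b = 0.5 gives +8%, b = 1.0 gives +3%.

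**Inference with the planned BCa interval**

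N = 508, 1,958 simulated trials per cell, 1,000 bootstrap samples, no covariates, no missing data, Monte Carlo SE about 0.6 points:

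| d, true b | result | without arm | with arm |
|---|---|---|---|
| 0.283, 0 | interval excludes zero | 9.0% | 7.0% |
| 0.283, 0 | of these, in H2 direction | 7.1% | 3.3% |
| 0.5, 0 | interval excludes zero | 12.5% | 7.5% |
| 0.5, 0 | of these, in H2 direction | 12.0% | 3.7% |
| 0.283, 0.254 | mean a×b (true 0.072) | 0.089 | 0.074 |
| 0.283, 0.254 | coverage | 94.9% | 95.2% |
| 0.283, 0.254 | interval excludes zero | 59.9% | 47.6% |

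The 0.5 SD rows are illustrative; the plan gives no arm difference in Z. A separate joint-significance simulation (1,500 trials, b = 0) shows the same pattern in the H2 direction: 4.7% without arm, 2.1% with arm.

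**The case against.** **Joint fitting was probably intended.** The plan's c' can come only from an outcome model with X and Z together. The mediation diagram (Figure 3) cannot be seen in the text available. Section 3.C.1.b reports earlier work by the team in which mediators removed a predictor's association with abstinence, which needs both in one model. This makes a drafting slip plausible. It does not settle the matter, because these points imply a joint model for c' and none says that b comes from it.

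**A non-zero c' is an inference.** That is right, and H2 does not say whether mediation is partial or complete. The inference rests on the intervention's stated targets and on the one-at-a-time analysis of mediators.

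**The percentage is soft.** This stands. It depends on the unstated scale of 0.14 and on how strong mediation is: from +35% to +3% as b goes from 0.14 to 1.0 at the planned arm difference. In absolute terms the planned-size bias in a×b is 0.013 log-odds, against a total effect of 0.809.

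**The effect on inference is small.** In part. Coverage at the planned effect is about 95% either way, and with b = 0 much of the excess over 5% remains with arm included. The contrast in the H2 direction, 7.1% against 3.3%, is due to the omission.

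**The sign rule has exceptions.** With opposite signs and a small b, the estimate can cross zero and end farther away: d = 0.5, b = 0.03, c' = −0.8 gives −0.061. When a is very small relative to b, omitting arm can shrink b slightly, by up to about 2%. Neither changes the fix.

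**Conclusion.** Wrong as written. The only instruction for path b leaves out treatment arm, and following it gives a biased mediated effect whenever PSFW+ changes the mediator and also affects quitting by another route. With a, b and c' all positive, as the trial's hypotheses and intervention content suggest, the bias favours H2. At the planned size it is modest: +18% in a×b, under my reading of 0.14 and the planned abstinence rates. The more serious consequence is with no true mediation, where false support for H2 about doubles. The direction and the remedy do not depend on the scale assumption; the percentages do. The point should be fixed before Aim 2 is analysed. It does not touch the Aim 1 primary analysis.

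**What to change.** In Section 3.C.6.c, state that b and c' are both estimated from one logistic model that always contains treatment arm, whatever the covariate screen selects:

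logit P(Y = 1) = b₀ + c'X + bZ + baseline covariates.

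Apply the same rule to the exploratory mediation analyses in Section 3.C.6.d.

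This costs one sentence and one model term, and needs no new data. The standard error of b rises by about 2% at the planned a (0.144 against 0.142). In the simulation the chance of declaring mediation at the planned effect falls from 60% to 48%. Part of the 60% is produced by the bias, so the difference is not all real power lost.

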Social support is a critical component of tobacco treatment.¹⁵ Research by our team and others has demonstrated the positive impact of social network participation on smoking cessation.¹⁶⁻¹⁹ **Smokers who participate in an online community – whether passively reading posts by others or actively engaging in online discussions – are more than twice as likely to achieve abstinence even after controlling for a broad range of covariates.**²⁰ Specifically for PLWH, an online community offers an anonymous and accessible platform to exchange support, to share information and cessation strategies, and potentially to overcome the loneliness and lack of network support for quitting which we have shown to be important drivers of smoking and obstacles to quitting.²¹⁻²³ Establishing a functional and therapeutically effective online community requires time, purposeful planning, and careful nurturing.²⁴⁻²⁶ Behavior intervention studies that have attempted to evaluate the effectiveness of online communities created synchronously with trial initiation have met with limited success.²⁷⁻²⁹ In preparation for this trial, The American Legacy Foundation (Legacy) – a partner on the proposal and leader in the field of online social networking for cessation – has already established and alpha and beta-tested a prototype online community including a core group of fully-trained seed users as an integrated component of PSFW (now “PSFW+”). These efforts ensure that by trial launch we will be prepared to achieve the following **Specific Aims** and test a priori hypotheses (H):

Aim 1. To test the efficacy of PSFW+ compared to an attention-matched web-health intervention (American Heart Association Getting Healthy) in achieving 7-day point prevalence abstinence (ppa) at 6 months post-randomization in a cohort of PLWH smokers (N=550). All subjects will be offered nicotine patches. *H1: PSFW+ will yield higher abstinence rates than the control intervention at 6 months.*

Aim 2. To examine whether the impact of treatment condition on cessation is **mediated by greater perceived social support** afforded by the PSFW+ program. This central aim is supported by our work with PLWH that has shown strong associations between loneliness, smoking, and lack of social support for quitting.^{22,23} *H2: Intergroup differences in 6-month abstinence will be mediated by greater changes in perceived social support among those in PSFW+.*

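### The Aim 2 path-b model, as worded, fixes neither treatment arm nor the mediator's baseline score, so b absorbs part of the direct treatment effect and a pretest decides whether it is a level or a change effect

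*Combined protocol and SAP*

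**What the plan says.** H2 in the Specific Aims reads "Intergroup differences in 6-month abstinence will be mediated by greater changes in perceived social support among those in PSFW". Section 3.C.6.c opens differently: "Aim 2 hypothesizes that greater social support mediates the intervention-cessation relationship". It then fixes the timing ("The 3-month assessment will be used for mediator"), so the mediator Z is analysed as a 3-month level, with 6-month abstinence as the outcome.

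The two path models are worded differently. The linear model for path a has "treatment arm as the main predictor, and covariates identified in bivariate analyses as being associated with social support". The logistic model for path b has Z as main predictor and "covariates identified in bivariate analyses as being associated with abstinence"; arm is not mentioned. The same section defines c' separately: it "is the regression path between treatment group and outcome controlling for the effect of the mediator". It does not say that b is taken from that model.

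Section 3.C.6.c gives no screening level. Section 3.C.6.a does: "baseline measures identified in bivariate analyses as statistically significantly (at the 0.05 level) associated with the outcome measures will be included". That section lists mediating variables separately from baseline measures, so it is unclear whether baseline support is a screening candidate at all.

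**The concern.** Randomisation protects path a but not path b, which is an observational association within the trial.

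- **Arm.** If PSFW+ raises support and also raises abstinence by other routes, a b-model without arm credits part of the direct effect to support. That can produce apparent mediation where there is none.
- **Baseline.** With the baseline score in the model, b measures the effect of change. Without it, b measures the effect of the 3-month level. Under a 0.05 screen, a noisy test on few quitters makes that choice.

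The Specific Aims call Aim 2 central, so its estimand should not depend on either point.

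**Working it through.** **1. The plan's own power figure.** Sample Size Considerations: Aim 2 gives a=b=0.14, N=508 and at least 80% power. Read as standardised linear coefficients with X=±1: 0.14×√508 = 3.155; Φ(3.155−1.96) = 0.884; both paths significant, 0.884² = 0.78. Simulation gives 79% with a percentile bootstrap and 85% with a bias-corrected bootstrap. The figure therefore reproduces on the linear scale with the interval family the plan names. Path b, however, is logistic. If 0.14 is a log-OR per SD, power for b alone is only about 9% to 11% (correlation 0.7 and 0.5), even with arm and baseline fixed.

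**2. Events.** 254×(0.075+0.154) = 58 quitters.

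**3. Set-up.** From the documents: 254 per arm, 7.5% and 15.4% abstinence, and a=0.14. Assumed:
- a=0.14 with X=±1 means an arm difference of 2×0.14 = 0.28 SD in Z.
- The correlation ρ of baseline (Z0) with 3-month score is 0.6 or 0.75.
- Baseline is screened by t-test against abstinence at 0.05.
- Path a always holds arm and baseline.
- Mediation is declared when a and b are both significant.

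Monte Carlo error is about 1 to 2 points. Paired values below are for ρ = 0.6 / 0.75.

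**4. Leaving arm out, mediator without effect.** Hand check: the direct log-OR is ln[(0.154/0.846)/(0.075/0.925)] = 0.81. The slope of arm on Z is 0.28×0.25/(1+0.28²×0.25) = 0.069. Their product is 0.056. Simulation agrees: b is about 0.06, with false mediation of 5% to 6%.

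If baseline also predicts abstinence (log-OR 0.3):

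| Path-b model | b | False mediation |
|---|---|---|
| As worded (no arm, baseline screened) | 0.12 / 0.15 | 11–12% / 13–14% |
| Arm in, baseline screened | 0.05 / 0.06 | 6–7% / 7% |
| Arm and baseline fixed | about 0 | 4–5% |

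The screen keeps baseline in about 55% of these trials. Forcing baseline in without arm still leaves b biased, by 0.085 / 0.12–0.13, so both terms are needed. If arm is itself screened, it stays in about 80% of trials and adds under 0.01 of bias.

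**5. Abstinence depends on change (0.44 per SD).** If baseline is left out, b shrinks by (1−ρ): 0.44×0.40 = 0.18 and 0.44×0.25 = 0.11. The screen keeps baseline in only 23–24% / 12% of trials.

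| Path-b model | b | Joint power |
|---|---|---|
| Arm and baseline fixed | 0.44–0.45 | 0.69 / 0.52 |
| As worded | 0.32 / 0.22 | 0.52 / 0.29 |
| Arm in, baseline screened | 0.26–0.27 / 0.17 | 0.38 / 0.18 |

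Part of the as-worded power comes from the upward bias in step 4. At ρ=0.3 the as-worded model loses nothing (0.79 against 0.75 fixed). A separate parameterisation without a direct effect gives 77% against 81%.

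**6. Only the 3-month level matters (0.44).** Fixing baseline leaves b unbiased. Joint power is 0.66–0.67 / 0.52–0.53, against 0.70–0.72 / 0.58–0.59 for the screened model with arm: a cost of about 4 to 7 points. Against a model with arm that never holds baseline, the cost is about 14 / 34 points.

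**7. With the planned BCa interval.** Under the null of step 4, false mediation is 7.8% / 5.8% with both terms fixed, 8.8% / 10.2% screened with arm, and 16% / 17% without arm. The pattern is the same.

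**The case against.** **Arm may already be intended.** The definition of c' implies a model with both arm and mediator, and Figure 3, which is not in the text available here, may show b and c' together. A reader might infer that the mediation analysis ignores arm altogether; the documents do not support that. What stands is that the path-b sentence omits arm where the path-a sentence names it, and nothing says that b comes from the c' model.

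**A level model is coherent.** The opening line of 3.C.6.c and the choice of the 3-month score fit it. H2 can also be read as an arm contrast, and under randomisation the expected arm difference in level equals that in change. That settles path a, not path b. It does mean that fixing baseline is partly a choice of estimand, with the cost in step 6.

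**A sharp loss of power is not established.** A reader might infer that screening baseline severely attenuates b. That needs a pure change model and a correlation of about 0.5 or more, which the documents do not give. A pure change model also implies a marginal baseline slope of 0.44×(ρ−1), or −0.18 / −0.11: those with less support at baseline quit more. The only related evidence points the other way. Section 3.C.1.c links greater loneliness to treatment failure, and 3.C.1.f reports less baseline loneliness among abstainers (P=0.09, which would itself fail a 0.05 screen). That evidence concerns loneliness, not general perceived support. The objection stands against any headline about power, but not against the bias from omitting arm.

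**Conclusion.** The point holds as a specification gap that matters most for bias. Followed literally, the path-b wording inflates b by about 0.06 with no mediator effect. When baseline support also predicts abstinence, b reaches about 0.12 / 0.15 and false mediation rises from 4–5% to about 11–14%. Most of that comes from omitting arm; with arm in and baseline screened, the harm under no mediator effect is small.

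The power consequence is conditional. If change drives abstinence, the wording loses about 17 points (0.69−0.52) / 23 points (0.52−0.29), and nothing at ρ=0.3. If only level matters, fixing baseline costs power instead. These sizes rest on the assumed correlation, the 0.28 SD arm effect, the assumed log-ORs and a 0.05 screen. Aim 1 is unaffected.

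**What to change.** In 3.C.6.c:

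- State that b and c' come from one logistic model that always contains treatment arm and the 3-month mediator.
- For mediators measured at baseline (general perceived support, smoking-specific support, loneliness), enter the baseline value of the same scale in both the a- and b-models, outside the bivariate screen. Since b·Z + d·Z0 = b·(Z−Z0) + (b+d)·Z0, the coefficient is then the same whether Z is entered as a score or as a change.
- Exempt the PSFW+ online-community support scale from the baseline term, because 3.C.4.b excludes prior PSFW+ users.
- Align the opening line with H2.

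In Sample Size Considerations: Aim 2, state the scale of a=b=0.14 and give the power for this model.

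**Cost.** This takes a few sentences and a recalculation. No new data are needed if the three scales are in the baseline battery; 3.C.5 lists visits rather than instruments by visit, but H2 presupposes a baseline score. The price is precision: the standard error of b rises from about 0.14 to 0.18 / 0.22. The b detectable with 80% power (2.80×SE) therefore rises from about 0.40 to 0.51 / 0.61. The plan should state this, together with the level-effect costs in step 6.

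The Amendment says that the parent study closed in 2020. If Aim 2 has already been analysed, report the arm- and baseline-adjusted estimate beside the screened one.
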